2.2 Rationale

The current standard of care is observation and quarantine after exposure to COVID-19. There is no approved treatment or prophylaxis for COVID-19.

As of March 6, 2020, the CDC estimates that the transmission of SARS-CoV2 after a U.S. household close contract is 10.5% (95%CI, 2.9 to 31.4%).⁹ Among all close contacts, the SARS-

PREP COVID-19

CoV2 transmission rate is estimated at 0.45% (95%Cl, 0.12 to 1.6%) by the CDC. These estimates are based on monitoring of travel-associated COVID19 cases. Conversely, in a setting with community transmission, the secondary attack rate in China was 35% (95%Cl, 27-44%) based on 48 transmissions among 137 persons in 9 index patients.

Chloroquine or Hydroxychloroquine may have antiviral effects against SARS-COV2 which may prevent COVID-19 disease or reduce disease severity. It is not known at what dosing hydroxychloroquine may be effective for pre-exposure prophylaxis.

We propose to dose for SARS-CoV-2 pre-exposure prophylaxis at:

- 1. 400mg once weekly (with a loading dose)
- 2. 400mg twice weekly (with a loading dose)

Study recruitment is expected to take 4 weeks, and all participants will be followed for a minimum of 4 weeks. If study recruitment is slower than anticipated, the study medications will be given for a maximum of 12 weeks.

The projected levels achieved will be approximately 0.72 uM which is at the half-maximal effective concentration (EC50) where 50% viral inhibition would occur. Given chloroquine's and hydroxychloroquine's long half-time, a steady-state concentration may take days to achieve. Thereby, a loading dose may be necessary as seen in emergency prophylactic use of hydroxychloroquine or chloroquine for anti-malarial purposes.⁴

If hydroxychloroquine does not prevent disease for some, it may reduce COVID-19 disease severity. Attenuated disease may, in turn, be associated with reduced rates of transmission.

2.3 Potential Risks and Benefits

2.3.1 Potential Risks

The short-term use of hydroxychloroquine is well-tolerated with a safe track record since 1955. The most common reported side effects include:

- headache, dizziness, ringing in your ears;
- nausea, vomiting, stomach pain;
- loss of appetite, weight loss;
- mood changes, feeling nervous or irritable;
- skin rash or itching;
- hair loss.

GI side effects are minimized when taken with a meal or with milk. Antacid medications should be spaced apart by at least 4 hours.

Long-term use of hydroxychloroquine at its accepted prophylactic dose is also well-tolerated.

In our recent post-exposure study of hydroxychloroquine, where hydroxychloroquine is given at high dose (800mg) daily for 5 days, 70% of participants reported no side effects. The most common side effects, reported in ~30% of participants were GI-related symptoms such as nausea or vomiting.

In this study, we are using lower dose (400mg) weekly or twice weekly. We expect even fewer side effects, if any.

- Potential adverse effects by system, as listed on the FDA package insert:
 - Eye: "Chloroquine retinopathy" is a rare side-effect of chronic use after multiple years of use. This has not occurred with <1 year of continuous use.
 Furthermore, based on the recommendation by the American Academy of Ophthalmology, screening for retinopathy is warranted with dosing higher than 5 mg/kg/day. The proposed dosing in this trial is order of magnitudes lower.
 - Dermatologic Reactions: Bleaching of hair, alopecia, pruritus, skin and mucosal pigmentation, photosensitivity, and skin eruptions (urticarial, morbilliform, lichenoid, maculopapular, purpuric, erythema annulare centrifugum, Stevens-Johnson syndrome, acute generalized exanthematous pustulosis, and exfoliative dermatitis).
 - **Hematologic Reactions**: Various blood dyscrasias such as aplastic anemia, agranulocytosis, leukopenia, anemia, thrombocytopenia (hemolysis in individuals with glucose-6-phosphate dehydrogenase (G-6-PD) deficiency).
 - **Gastrointestinal Reactions:** anorexia, nausea, vomiting, diarrhea, and abdominal cramps. Isolated cases of abnormal liver function and fulminant hepatic failure.
 - **Cardiac Reactions:** Long-term use (>1 year) has been associated with the development of cardiomyopathy and arrhythmias.
 - Allergic Reactions: Urticaria, angioedema, and bronchospasm have been reported
 - **CNS Reactions**: Irritability, nervousness, emotional changes, nightmares, psychosis, headache, dizziness, vertigo, tinnitus, nystagmus, nerve deafness, convulsions, ataxia
 - **Miscellaneous Reactions:** Weight loss, lassitude, exacerbation or precipitation of porphyria and non-light-sensitive psoriasis.

2.3.2 Known Potential Benefits

- There are no known benefits in humans for preemptive treatment.
- *In vitro* antiviral activity against SARS-CoV and SARS-CoV-2 viruses.
- Chloroquine and Hydroxychloroquine have a long history of safe, effective use as an antimalarial, both acutely and long-term use.
- Chloroquine is being used therapeutically for severe COVID-19 disease in China and Korea.
- Commonly used as a chronic medication for autoimmune disorders (rheumatoid arthritis, systemic lupus erythematosus).

• Recent studies have shown potential broad antiviral effects *in vitro* at dosages below currently recommended clinical dosing, reducing risk of potential adverse effects listed above.

3 OBJECTIVES

3.1 Study Objectives

To determine if pre-exposure prophylaxis with hydroxychloroquine is effective at prevention of COVID-19 disease.

3.2 Study Outcome Measures

3.2.1 Primary Outcome Measure

[figure not shown]
• COVID-19-free survival

3.2.2 Secondary Outcome Measures

- Incidence of confirmed SARS-CoV-2 detection
- Incidence of symptoms compatible with COVID19 (possible disease)
- Incidence of all-cause study medicine discontinuation or withdrawal
- Ordinal Scale of COVID-19 Disease Severity (for those who develop COVID-19)
 - No illness
 - Illness with outpatient observation
 - Hospitalization (or post-hospital discharge)
 - Hospitalization with ICU stay or death
- Incidence of hospitalization or death
- Self-reported adherence
- Self-reported study medication side effects

Primary outcome of COVID-19-free survival will be confirmed by positive test. Assessment of other outcome measures will be primarily by self-report. As necessary, COVID-19 disease will be verified from public health records, medical records, or death certificates.

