Secondary Endpoints	 Incidence of confirmed SARS-CoV-2 detection Incidence of possible COVID19 symptoms Incidence of all-cause study medicine discontinuation Ordinal Scale of COVID-19 Disease maximum severity if COVID-19 diagnosed Incidence of Hospitalization for COVID-19 or death Incidence of study medication-related side effects 	
Duration of Participation	• Recruitment and follow up will be internet-based. All patients will be followed for at least 4 weeks. Recruitment is expected to take 4 weeks, for a total study duration of 8 weeks. But the total study duration will depend on the actual rate of enrollment. Study drug will be given for a maximum of 12 weeks.	
Inclusion Criteria	 Healthcare worker, at high risk of COVID-19 exposure: Persons primarily working in emergency departments (physicians, nurses, ancillary staff, triage personnel) Persons primarily working in intensive care units (physicians, nurses, ancillary staff, respiratory therapists) Persons performing aerosol generating procedures: ex. Anesthesiologists, nurse anesthetists (CRNAs) First responders: ex. EMTs, paramedics 	
	 Age >=18 years of age Provision of Informed Consent 	
Exclusion Criteria	 Active COVID-19 disease Confirmed prior COVID-19 disease Current fever, cough, shortness of breath Contraindication or allergy to chloroquine or hydroxychloroquine Prior retinal eye disease Known Chronic Kidney disease, Stage 4 or 5 or dialysis. Known glucose-6 phosphate dehydrogenase (G-6-PD) deficiency. Weight <40 kg Current use of hydroxychloroquine or cardiac medicines of flecainide, amiodarone, digoxin, procainamide, or propafenone Current use of medications with known significant drug-drug interactions: artemether, lumefantrine, mefloquine, tamoxifen, or methotrexate. 	

Statistical	 10% transmission rate for high-risk healthcare workers with		
Assumptions	no treatment		
	 Alpha = 0.025 (to account for two treatment groups vs. placebo comparisons) Assuming 15% lost to follow up in the placebo group and 5% lost to follow up in each treatment group N=3500 has 80% power to detect a hazard ratio of 0.65, using a two-sided log-rank test 		

Schematic of Study Design:

At the close of the study, any participant with ongoing illness will continue to be assessed for up to a total of 90 days after the common closing date.

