10 STATISTICAL CONSIDERATIONS

10.1 Study Hypotheses

We hypothesize that Hydroxychloroquine is superior to placebo for preventing COVID-19 disease. We hypothesize, that if COVID-19 develops while a person is taking hydroxychloroquine prophylaxis, then the COVID-19 disease would be less severe.

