10.4 Final Analysis Plan

We will assessCOVID-19-free survival in high-risk healthcare workers who receive hydroxychloroquine compared to those who receive placebo.

We will compare survival in a time-to-event analysis for COVID-19-free survival using Log-rank test with survival displayed as a Kaplan-Meier curve. Analysis will be intention-to-treat. Persons who develop confirmed COVID-19 or die will be considered failures. Persons lost to follow up will be censored.

Secondary endpoints for incidence will be assessed via Fisher's Exact test for the proportions by study arm. The secondary endpoint on the ordinal scale will be assessed with a proportional odds model.

PREP COVID-19

Version 1.0 27 March 2020

Among those with symptoms, severity of symptoms (recorded on a 0-10 visual analog scale) will be compared via Mann-Whitney U by study arm.

A priori subgroup analyses will include assessment by:

- Days from Exposure
- Decile of age
- Sex as a biological variable
- Censored subjects, who became symptomatic before receipt of the first dose of study medicine, will be separately analyzed and reported.

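### Ordinal severity and the 0-10 symptom score are compared by arm only among people who fall ill; if prevention depends on would-be severity, these tests can mislead about attenuation

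*Combined protocol and SAP*

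**What the plan says.** The combined protocol and SAP restricts both severity measures to people who become ill.

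- **Ordinal scale.** The Summary lists "Ordinal Scale of COVID-19 Disease maximum severity if COVID-19 diagnosed". Section 3.2.2 has the same restriction: "Ordinal Scale of COVID-19 Disease Severity (for those who develop COVID-19". Section 10.4 names the test and does not widen the population: "The secondary endpoint on the ordinal scale will be assessed with a proportional odds model".
- **Symptom score.** Section 10.4: "Among those with symptoms, severity of symptoms (recorded on a 0-10 visual analog scale) will be compared via Mann-Whitney U by study arm".
- **Hypothesis.** Section 10.1 states attenuation conditionally: "if COVID-19 develops while a person is taking hydroxychloroquine prophylaxis, then the COVID-19 disease would be less severe". Section 2.2 voices the same hope.
- **A severity outcome not restricted to cases.** Section 3.2.2 lists "Incidence of hospitalization or death", and section 10.4 says "Secondary endpoints for incidence will be assessed via Fisher's Exact test for the proportions by study arm".

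The intention-to-treat statement in 10.4 sits in the paragraph on the primary time-to-event analysis and does not lift these restrictions. The plan has no all-randomised analysis of the ordinal scale, no sensitivity analysis for the conditional question, and no caution on how to read the restricted comparisons.

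**The concern.** The trial is powered on the drug changing who becomes a case (hazard ratio 0.65, section 10.2). If it does, cases on drug and cases on placebo are not comparable groups, because membership is decided after randomisation by the event under study. A difference in severity between them can then reflect which cases were averted rather than any change in the illness of those who still fell ill.

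The error can go either way. If the averted cases are mostly mild, the remaining cases on drug look more severe although nobody was made worse. If the averted cases are disproportionately severe, the remaining cases look milder. In that second situation severe illness really does fall, and the error is to credit attenuation instead of prevention.

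What is at stake is the second hypothesis in 10.1, since readers would look to these two comparisons for evidence on it.

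**Working it through.** The plan gives no figure for these comparisons, so there is none to reproduce. The check asks how far a cases-only comparison can move when the drug changes nobody's severity.

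**Inputs from the document**
- Placebo risk 10%, hazard ratio 0.65, 1165 per arm (10.2).
- Severity mix 80% mild to moderate, 14% severe, 6% critical, in laboratory-confirmed patients generally (2.1).

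**Assumptions**
- Severe plus critical (20%) is treated as hospitalised.
- Two-sided 0.025, because 10.4 sets no alpha for secondary outcomes.
- No loss to follow-up at first.

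**Case numbers.** Risk on drug = 1 − 0.90^0.65 = 0.0662. Expected cases are 1165 × 0.10 = 116.5 on placebo and 1165 × 0.0662 = 77.1 on each active arm. Averted risk = 0.10 − 0.0662 = 0.0338. The three arms sum to 116.5 + 77.1 + 77.1 = 270.7, not the roughly 310 events given in 10.2; nothing below uses the 310.

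**Cases-only odds ratio.** Placebo has 0.08 mild and 0.02 severe. Let m be the share of averted cases that are mild. On drug:
- severe = 0.02 − 0.0338(1 − m)
- mild = 0.08 − 0.0338m
- odds ratio = (severe/mild) ÷ (0.02/0.08)

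Example, m = 0.9: severe = 0.0166, mild = 0.0496, odds ratio = 0.335/0.25 = 1.34.

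| m | severe averted | mild averted | cases-only OR | significant, worse on drug | significant, milder on drug |
|---|---|---|---|---|---|
| 1.0 | 0% | 42% | 1.73 | about 27% | about 0% |
| 0.9 | 17% | 38% | 1.34 | about 8% | about 0.1% |
| 0.8 | 34% | 34% | 1.00 | about 1% | about 1% |
| 0.7 | 51% | 30% | 0.70 | about 0.1% | about 8% |
| 0.6 | 68% | 25% | 0.43 | 0% | about 35% |

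The last two columns are simulated (20,000 trials per row, severe split 14:6). A tie-corrected rank test stands in for the proportional odds test. With the losses assumed in 10.2 (15% placebo, 5% active), the 8% figures become about 7.5% and the extremes about 24% and 33%.

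**Sensitivity to the severity mix.** With 14% of cases severe, the odds ratio is 1.17 at m = 0.9, 1.00 at m = 0.86 (proportional) and 0.75 at m = 0.8.

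**What an all-randomised comparison can show.** With proportional prevention and no attenuation, exact Fisher power at 0.025 is:
- hospitalization or worse, 2.0% v 1.32%: 13%
- ICU or death, 0.6% v 0.40%: 3%

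The pooled all-randomised ordinal test favours the drug in about 74% of trials at m = 1.0, where severe disease is not reduced at all. It is driven by incidence and cannot carry a statement about severity.

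**Symptom score.** The document gives no distribution for it, so no magnitude is offered. People with symptoms are also a wider group than COVID-19 cases, since 3.2.2 counts compatible symptoms as possible disease. The ordinal figures therefore do not carry over.

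**The case against.** Four points can be made for the plan.

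- **The hypothesis is conditional, so a conditional comparison fits it.** This explains the choice, but it does not make a comparison among cases a randomised one. It does stand against the remedy in one respect: an all-randomised analysis measures prevention plus attenuation and does not by itself test the hypothesis in 10.1.
- **Hospitalization or death is already compared without restriction to cases.** This largely stands. That endpoint is close to the hospitalization-or-worse cut-point, so the gap is narrower than it first looks. Still missing are an all-randomised ICU-or-death comparison, a rule on which result supports a severity statement, and a caution on the restricted tests.
- **The distortion is speculative.** In part. It needs prevention to depend on how severe the case would have been. The document gives no reason to expect that and none to rule it out.
- **The scale has a No illness level, so an all-randomised analysis may have been meant.** That level has little use among cases and does suit all participants, but the Summary and 3.2.2 both limit the scale to cases.

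A reader might also infer that the all-randomised test is the better detector of attenuation. It is not. With attenuation and no prevention (10% cases in both arms), Fisher's test on hospitalization or worse has about 25% power against 35 to 36% for the cases-only test at a severity odds ratio of 0.5, and about 5% against 7 to 8% at 0.75. The case for it is that it keeps the randomisation, not that it has more power.

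**Conclusion.** The concern holds in limited form. Both comparisons use groups selected after randomisation by events the drug is meant to prevent, and they can mislead if the drug prevents cases unevenly across severity. At moderate unevenness, the cases-only odds ratio is 1.34 or 0.70 with a misleading significant result in about 8% of trials. The 27% and 35% figures need every averted case to be mild, or about 68% of severe cases to be averted. All of this rests on the general-patient severity mix in 2.1, on equating severe with hospitalised, and on an assumed alpha.

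Three stronger readings are not supported:
- that these comparisons will be biased: with proportional prevention the odds ratio is 1.00 and the error rate nominal, and with no prevention the problem is absent;
- that the plan has no randomised evidence on severity: hospitalization or death provides some;
- that the main result is at risk: the primary analysis, its alpha and the sample size are untouched.

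This is a cheap improvement to secondary analyses.

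**What to change.** In section 10.4:

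1. Add an ordinal analysis in all randomised participants with No illness as the lowest level, and report the odds ratio at each cut-point (any illness; hospitalization or worse; ICU or death).
2. Base any randomised statement about severe disease on the hospitalization-or-worse cut-point, with ICU or death as supportive, and not on the pooled odds ratio.
3. State that this measures the total effect on severe disease, prevention plus any attenuation, and does not by itself test the conditional hypothesis in 10.1.
4. Keep the cases-only ordinal and symptomatic-only 0-10 comparisons, labelled descriptive and not evidence of attenuation.
5. State how participants lost to follow-up are handled; do not score them as No illness by default. This matters because 10.2 assumes 15% loss on placebo and 5% on drug.

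Align the Summary and 3.2.2 with this text. Separately, reconcile the Summary's "Incidence of Hospitalization for COVID-19 or death" with 3.2.2, which does not limit the cause of hospitalization.

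The cost is text changes and one added analysis, with no new data. The downside is low power at the upper cut-points if the drug only prevents cases (13% and 3% at 0.025), and a conditional question that is answered only descriptively.

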4 STUDY DESIGN

At the close of the study, any participant with ongoing illness will continue to be assessed for up to a total of 90 days after the common closing date.

4.1 DESIGN

Randomized, double-blind clinical trial, parallel design. This is an event-driven trial. Subjects will be followed until study termination. Study drug will be prescribed for up to 12 weeks.

4.2 Study participant duration

- Weekly internet-based virtual visits for the duration of follow up
- Study drug is prescribed to be taken for up to 12 weeks
- For participants ill with COVID-19 disease at the common closing date for the study, observational follow up will extend to up to 90 days after the common closing date to assess final outcome status.

• Pregnant women have their fetal outcome assessed post-partum.

4.3 Study procedures

- 4.3.1 Screening
 - Baseline screening for eligibility via self-administered questionnaire
 - Informed consent

4.3.2 Randomization

- Participants will be randomized at the investigation pharmacy
- The investigational pharmacy will dispense masked study medicine (hydroxychloroquine or placebo)
- The study medicine will be shipped to participants to arrive ~1 day after enrollment
- 4.3.3 Day 1 Virtual visit
 - Verify receipt of study medicine
 - Clinical status check-in
 - Begins taking study medicine (2 tabs), then 2 tabs in 6-8 hours
 - Query for symptom status
 - Query for hospitalization or SAEs
- **4.3.4** Weekly Virtual visit
 - Clinical status check-in for COVID-19 symptoms
 - Assessment of adherence and side effects by self-report
 - Continue study medicine up to 12 weeks
 - Query for study medicine side effects since enrollment
 - Query for SARS-CoV-2 testing
 - Query for hospitalization or SAEs
- **4.3.5** Study termination virtual visit (to be completed on or shortly after the common closing date for the study)
 - Clinical status check-in for COVID-19 symptoms
 - Query for study medicine adherence and side effects since enrollment
 - Query for SARS-CoV-2 testing
 - Query for hospitalization or SAEs
 - Query for pregnancy status
 - Final outcome assessment
- **4.4** Individually identifiable health information: Name, date of birth, and phone number will be collected so as to prescribe study medication. Email addresses will be collected for communication. If participants are hospitalized, the hospitalization date will be collected.

4.5 Sub studies

Participants in Minneapolis, MN, Portland, OR, and Nashville TN, will have the opportunity to participate in an optional sub-study evaluating peripheral blood correlatives. Please see full details in Appendix A.

5 STUDY ENROLLMENT AND WITHDRAWAL

Participants will undergo screening via internet-based google forms. The screening and inclusion criteria will be based on self-report.

5.1 Subject Inclusion Criteria

- A healthcare worker at high risk for COVID-19 exposure (defined below)
- >= 18 years of age
- Provision of informed consent

5.2 Subject Exclusion Criteria

- Active COVID-19 disease
- Confirmed prior COVID-19 disease
- Current fever, cough, shortness of breath
- Contraindication or allergy to chloroquine or hydroxychloroquine
- Prior retinal eye disease
- Known Chronic Kidney disease, Stage 4 or 5 or dialysis.
- Known glucose-6 phosphate dehydrogenase (G-6-PD) deficiency.
- Weight <40 kg
- Current use of hydroxychloroquine or cardiac medicines of flecainide, amiodarone, digoxin, procainamide, or propafenone
 - Current use of medications with known significant drug-drug interactions:

artemether, lumefantrine, mefloquine, tamoxifen or methotrexate.

Rationale for inclusion / exclusion criteria:

Healthcare workers at high risk for COVID-19 exposures include:

- Persons primarily working in emergency departments (physicians, nurses, ancillary staff, triage personnel)
- Persons primarily working in intensive care units (physicians, nurses, ancillary staff, respiratory therapists)
- Persons performing aerosol generating procedures: ex. Anesthesiologists, nurse anesthetists (CRNAs)
- First responders: ex. EMTs, paramedics

In clinical practice of tropical medicine, chloroquine or hydroxychloroquine are prescribed without any baseline laboratory testing or monitoring.

Age criteria are meant to increase the propensity to follow up and minimize dropouts.

Chronic use of hydroxychloroquine for >1 year can cause retinopathy or cardiomyopathy, thus persons with baseline conditions will be excluded. Study medicine is excreted via the kidney with dose reduction recommended in CrCl <30 cc/min (Stage 4 Kidney Disease). G-6-PD deficiency is listed as a caution on the FDA label. G-6-PD testing is not routinely performed in clinical care prior to giving hydroxychloroquine prescriptions (unlike with primaquine). Medication exclusions are for possible drug-drug interactions, particularly with cardiac arrhythmia medicines with a caution on the FDA-package insert.

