6.2 Dosage, Preparation, and Administration of Investigational Product

6.2.1 Drug/Device Handling: Hydroxychloroquine or placebo will be dispensed by the investigational Pharmacy. To do so, study investigators will send a prescription to the Pharmacy, the pharmacy will randomize the subject, and dispense the appropriate study medicine. The medicine will then be provided to research volunteers via courier delivery in the United States.

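### The rationale in 5.2 says people with baseline cardiomyopathy are excluded, but neither exclusion list contains that criterion

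*Combined protocol and SAP*

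**What the plan says.** The explanatory text under the criteria in section 5.2 gives this reason for the organ-related exclusions: "Chronic use of hydroxychloroquine for >1 year can cause retinopathy or cardiomyopathy, thus persons with baseline conditions will be excluded". The sentence names two conditions, and the phrase about baseline conditions can only refer to those two.

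The list above that text, and the matching list in the Summary, each contain the item "Prior retinal eye disease". Neither contains cardiomyopathy, heart failure or any other cardiac diagnosis. The only item that mentions the heart excludes current users of five drugs (amiodarone, digoxin, flecainide, procainamide, propafenone). The same paragraph explains it on other grounds: "Medication exclusions are for possible drug-drug interactions, particularly with cardiac arrhythmia medicines with a caution on the FDA-package insert".

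On risk, section 2.3.1 says of retinopathy: "This has not occurred with <1 year of continuous use". Of the heart it says: "Long-term use (>1 year) has been associated with the development of cardiomyopathy and arrhythmias". Section 4.1 limits exposure: "Study drug will be prescribed for up to 12 weeks".

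On screening, section 5 says: "The screening and inclusion criteria will be based on self-report". Section 6.2 adds that "study investigators will send a prescription to the Pharmacy" before dispensing, but describes no medical review at that step.

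**The concern.** In a remote trial, the exclusion list is what keeps unsuitable people out. The rationale commits the trial to excluding two groups, and the list acts on one of them. If sites, the pharmacy and the web form follow the list, people whom the protocol says are excluded can be randomised to the drug.

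Later detection is unlikely. Clinical evaluations are by self-report (7.1), the main protocol has no laboratory evaluations (7.2), and no physical examination or ECG is described anywhere. Adverse events are recorded only if they lead to hospitalisation (8.2.1). What is at stake is participant safety and the consistency of an eligibility rule. The efficacy analysis is not affected.

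**Working it through.** No power or alpha figure is involved, so the check is a comparison of texts plus simple arithmetic on exposure.

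**1. Conditions in the rationale against criteria in the lists**

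| Condition named in the 5.2 rationale | Item in the 5.2 list | Item in the Summary list |
|---|---|---|
| Retinopathy | Yes, 1 of 10 | Yes, 1 of 10 |
| Cardiomyopathy | None, 0 of 10 | None, 0 of 10 |

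Both lists are intact and have the same items, so a broken table or a redaction does not explain the gap.

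**2. Could another item catch the same people?**

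- *Cardiac medicines.* This item removes anyone taking one of the five drugs, whatever the diagnosis, and so will catch some people with cardiomyopathy. It leaves those who take none of the five.
- *General item on contraindication or allergy.* The documents do not define the contraindications and never call cardiomyopathy one. Section 2.3.1 lists it only as an effect of long use. The protocol also lists retinal disease, G-6-PD deficiency and stage 4 or 5 kidney disease separately, so it does not rely on the general item for specific conditions.
- *Current fever, cough or shortness of breath.* Someone with compensated cardiomyopathy may have none of these.

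The group left over is people with known cardiomyopathy who take none of the five drugs, have no current respiratory symptoms or fever, and do not themselves regard the condition as a contraindication.

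**3. Could another step catch them?**

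Screening is a self-administered web form (sections 5 and 6.7). The form is not in the documents, so whether it asks about heart disease is unknown. The investigator's prescription (6.2) comes with no described review of medical history.

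**4. Exposure against the threshold the protocol cites**

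- Maximum duration: 12 weeks × 7 = 84 days. As a share of one year: 84 / 365 = 0.230, about 23%.
- Cumulative dose: an 800 mg load (2 × 400 mg) plus later doses of 400 mg. The range depends on whether the loading week counts as week 1.
  - Weekly arm, 11 to 12 later doses: 800 + 11 × 400 = 5,200 mg, to 800 + 12 × 400 = 5,600 mg.
  - Twice-weekly arm, 22 to 24 later doses: 800 + 22 × 400 = 9,600 mg, to 800 + 24 × 400 = 10,400 mg.

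The documents give no cumulative-dose threshold for cardiac toxicity, so the dose totals only describe exposure.

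**5. Does short exposure justify treating the two conditions differently?**

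The rationale applies the same one-year threshold to both. Section 2.3.1 goes further for the eye and says the harm has not been seen below one year, yet prior retinal disease is still excluded. The short-exposure argument would remove the retinal criterion as readily as it would excuse the missing cardiac one.

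**The case against.** The strongest reply is that the two lists agree item for item and the outlier is one explanatory sentence. On that view the sentence may be too broad, and the remedy would be to limit it to retinal disease instead of adding an exclusion that costs some eligible participants. The documents do not show which text was the slip, and narrowing the sentence would remove the inconsistency. But it would also drop a stated safety exclusion while keeping the retinal one that rests on the same reasoning. Adding the criterion is the option that matches the stated intent.

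A second reply is that little harm would follow. The protocol links cardiomyopathy to use beyond one year, and it gives no risk figure for short use in people who already have the condition. There are also weekly queries on side effects, hospitalisation and serious events (4.3.4), a sick-visit form and an on-call physician (6.12), and freedom to stop the drug for substantial side effects (6.3). This stands as a limit on severity. These measures act only after dosing has begun, however, and would not identify the condition at entry.

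A third reply is that respondents are healthcare workers and the unseen form may ask. Both are possible. They make actual enrolment of such a person uncertain, but they do not replace a written criterion.

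**Conclusion.** The inconsistency is real and concerns an operative eligibility rule. Of two conditions the rationale says are excluded, one has a criterion in both lists and the other has one in neither. Confidence in the mismatch is high.

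The practical consequence is less certain. It depends on the content of the screening form and on how applicants read the general contraindication item. The gap is confined to people who escape the drug list and the symptom item. The documents do not give their number, and no estimate is made here. Expected harm is probably small at no more than 84 days of dosing. The point should be corrected because it concerns a safety exclusion in a self-report trial with an accrual ceiling of 3500 and because the correction is cheap.

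**What to change.** Add *Known cardiomyopathy* as an exclusion in section 5.2 and in the Summary, and make sure the self-report screening form asks about it directly.

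The cost is one line in each of two lists and at most one more question on the form. Some otherwise eligible people would be lost, a number the documents do not allow to be estimated. No endpoint, alpha level or power assumption changes.

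If the sponsor did not intend this exclusion, the rationale should be restricted to retinal disease, with a reason for treating the two conditions differently.
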